REACH P2: Communication Coaching to Improve Patient and Clinician Satisfaction in Cardiology Encounters

NCT Number: NCT03464110

Date: 12.14.18

Protocol Title Communication Coaching to Improve Patient and Clinician Satisfaction in Cardiology Encounters

Purpose of the study

Aim 1: Determine the effect of a clinician communication coaching intervention versus control on an objective measure of the quality of communication (primary outcome) and patients' perceptions of the quality of patient-centered care (secondary outcome), both overall and within Black and White patients.

Hypothesis 1a: As compared to the control group, the intervention will improve objective measures of communication quality in encounters with both Black and White patients combined and in each race subgroup.

Hypothesis 1b: Black patients and White patients seen by clinicians in the intervention group will report improvements in the quality of patient-centered care compared to patients seen by control group clinicians.

Aim 2: Determine the effect of a clinician communication coaching intervention versus control on racial disparities in objective measures of communication quality (primary outcome) and in the quality of patient-centered care (secondary outcome).

Hypothesis 2a: Racial disparities in objective measures of communication quality will be reduced in encounters with clinicians in the intervention group as compared to encounters with control group clinicians.

Hypothesis 2b: Racial disparities in patients' perceptions of the quality of patient-centered care (IPC score) will be reduced among those having encounters with clinicians in the intervention group as compared to encounters with clinicians in the control group.

Research Abstract

We propose to conduct a cluster randomized controlled trial of a clinician communication coaching intervention in ambulatory cardiology practices. The aim is to determine the effect of a clinician communication coaching intervention versus control on an objective measure of the quality of communication and patients' perceptions of the quality of patient-centered care, both overall and within Black and White patients. We will recruit cardiology clinicians and randomly assign them to the intervention or control arms. We will enroll their adult patients pre-intervention and post-intervention

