### F.3 Aim 2 Analyses:

*Hypothesis 2a:* Racial disparities in objective measures of the quality of communication will be **lower** in encounters with clinicians in the intervention group as compared to encounters with clinicians in the control group.

*Hypothesis 2b:* Racial disparities in patients' perceptions of the quality of patient-centered care will be **lower** among those seen by clinicians in the intervention group as compared to encounters with clinicians in the control group.

A mixed-effects Poisson model will again be the primary modeling strategy for the objective communication outcome Aim 2 analyses. For this Aim, however, the model will include patientrace interaction terms and will have the following form:  $\log(\lambda_{ik}) = \lambda_0 + \lambda_1(\text{Black}_i) + \lambda_2(\text{int}_k) + \lambda_3(\text{Black}_i * \text{int}_k) + \lambda_4(\text{premean}_k) + \lambda_5(\text{clinsex}_k) + \lambda_6(\text{clintype}_k) + b_{0k}$ , where  $Y_{ijk}$  is the number of quality communication statements for patient  $i$  in the post-period clustered within physician  $k$ , and  $Y_{ik}$  is assumed to be Poisson with mean and variance equal to  $\lambda_{ik}$ . Again, the random intercept  $b_{0k}$  is normally distributed and account for dependence of encounters within clinicians. In this model,  $\text{Black}_i$  is the indicator variable for whether a patient is Black (value of 1) or White (value of 0).

Post-treatment, the Black-white mean difference among patients seen by usual care group clinicians is  $BW_{uc} = \exp(\lambda_0 + \lambda_1) - \exp(\lambda_0)$ , **this represents the racial disparity in communication quality**. The B-W mean difference among patients seen by intervention group clinicians is  $BW_{int} = \exp(\lambda_0 + \lambda_1 + \lambda_2 + \lambda_3) - \exp(\lambda_0 + \lambda_2)$ .

Hypothesis 2a will be tested by  $\lambda_5$  being significantly greater than zero, indicating a greater mean number of quality communication statements for the intervention group versus the control group for Black patients as compared to White patients (i.e., the intervention group reducing the racial disparity). The estimated incident rate ratio, p-value, and 95% confidence intervals will be calculated via estimate statements in PROC GLIMMIX.

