A similar linear mixed-effects model (rather than a Poisson) model will be used to examine the reduction in racial disparities of quality of patient-centered care and test Hypothesis 2b. Note that in a linear model framework, the coefficients will represent differences in means rather than rate ratios.

Power and Sample Size Considerations: The effect of interest for Aims 1 and 2 is the relative difference in the post-period between the intervention and usual care groups; Aim 1 focuses on the overall difference and the difference within Black and White patients separately, while Aim 2 on the difference within Black patients compared to White patients. The sample size requirements are greatest for Aim 2; as discussed by Leon and Heo (2009), the needed

sample size for the patient race-by-intervention group interaction is 4 times that needed for the overall test. For Hypotheses 1a and 2a, our sample size calculations are based upon the difference between two Poisson rates (incident rate ratio) in a cluster randomized design (i.e., patients clustered within clinician).

Based on preliminary studies, the baseline mean number of quality communication statements is 1.0, and a conservative range of coefficients of variation (CV) is 0.2 to 0.5 to account for patients clustered within clinician. With a **sample size of 240 patients in the post period (6 per clinician)** and a type-I error of 5%, we will have 80% power to detect incident rate ratios of 1.5 to 1.8 for Hypothesis 1a in the overall test, 1.6 to 1.9 for Black or White patients separately, and 1.8 to 2.5 for Hypothesis 2a.

For hypotheses 1b and 2b, our sample size calculations are based upon the difference between two means in a cluster randomized design. We present a conservative range of intraclass correlation coefficients (ICC) to account for patients clustered within clinician. With a **sample size of 240 patients (6 per clinician)** and a type-I error of 5%, we will have 80% power to detect mean differences of effect size 0.37 to 0.44 for Hypothesis 1b in the overall test, 0.52 to 0.56 for Black or White patients separately, and 0.65 to 0.91 for Hypothesis 2b. PASS 15 was used for all calculations.

	Number of clinicians	Number of patients in the postintervention phase (number per clinician)	Hypothesis 1a and 2a: Incident Rate Ratio		Hypothesis 1b and 2b: Mean Effect Size	
			CV	Pre-post Relative Rate	ICC	Pre-post Difference

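### Hypothesis 2a names the wrong coefficient (λ5 for λ3), and a positive interaction is read as a reduced disparity although the change in the Black-White gap is never estimated

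*SAP*

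**What the plan says.** SAP F.3 (Aim 2 Analyses) fits a Poisson mixed model to post-period counts. Its coefficients are λ1 Black, λ2 intervention, λ3 Black-by-intervention, λ4 pre-period clinician mean, λ5 clinician sex and λ6 clinician type.

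The section writes the usual-care disparity as BWuc = exp(λ0+λ1) − exp(λ0) and says "this represents the racial disparity in communication quality". BWint has the same form for the intervention arm. Hypothesis 2a is that the disparity will be lower with intervention clinicians.

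The decision rule is λ5 "being significantly greater than zero, indicating a greater mean number of quality communication statements for the intervention group versus the control group" for Black relative to White patients, with the gloss "i.e., the intervention group reducing the racial disparity". The planned output is: "The estimated incident rate ratio, p-value, and 95% confidence intervals will be calculated via estimate statements in PROC GLIMMIX".

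The SAP's power section puts the effect on a relative scale: "The effect of interest for Aims 1 and 2 is the relative difference in the post-period between the intervention and usual care groups". It gives detectable rate ratios of "1.6 to 1.9 for Black or White patients separately" and "1.8 to 2.5 for Hypothesis 2a".

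The Protocol's Aim 2 lists "racial disparities in objective measures of communication quality (primary outcome") as its target. Its own F.3 uses the same gloss, but with a different model in which coefficient 5 is the three-way term for time, race and intervention.

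**The concern.** There are two faults. The first is a label: read literally, the SAP tests Hypothesis 2a on clinician sex. The index fits the Protocol's model and seems to have been kept when the SAP's model changed.

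The second is the reading of a significant result. The disparity is defined as a gap between two means, but the conclusion that it fell rests on one log-scale coefficient. The quantity that would show a fall, BWint − BWuc, is not planned as an output. The Protocol bases its main conclusions on the pre-specified hypotheses, so the gloss would allow a published statement that the disparity was reduced when the reported rate ratio cannot show whether the gap shrank, reversed or was there at all.

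**Working it through.** **Inputs.** From the SAP: 20 clinicians per arm; 6 post-period encounters each, taken as 3 Black and 3 White; mean count 1.0; between-clinician CV 0.2, 0.35, 0.5; detectable interaction 1.8 to 2.5; race-specific rate ratios 1.6 to 1.9. From the Protocol: two-sided 0.05. Assumed: R, the usual-care Black:White ratio of means. The Protocol's background gives a direction only, so R is varied. Also r = exp(λ2), the White-patient rate ratio, and g = exp(λ3).

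**1. The plan's own figure.** For two Poisson rates with clustering, clinicians per arm = 1 + (1.96+0.842)² × [(1+L)/m + CV²(1+L²)]/(L−1)². Set this to 20 and solve for L:
- m = 2: 1.81, 1.92, 2.09 for the three CVs (SAP: 1.8, 1.9, 2.1).
- m = 1: 2.19, 2.30, 2.47 (SAP: 2.2, 2.3, 2.5).

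The SAP's range is reproduced.

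**2. The gap implied by λ3.** With the usual-care White mean at 1.0, BWuc = R − 1 and BWint = r(R×g − 1).
- Reversed and larger in size when R > (r+1)/(r×g+1). For r = 1.0 this is 2/2.8 = 0.71 at g 1.8 and 2/3.5 = 0.57 at g 2.5. For r = 1.5 it is 2.5/3.7 = 0.68 and 2.5/4.75 = 0.53.
- Larger without reversing when R < (r−1)/(r×g−1). At g 1.8 this is 0.5/1.7 = 0.29 (r 1.5) or 0.8/2.24 = 0.36 (r 1.8).

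**3. How often a significant trial misleads.** Simulation with 40,000 trials per scenario, a gamma clinician effect and Poisson counts; λ3 is the log ratio of arm-by-race totals, significant if z > 1.96. The clinician effect cancels within clinician, so CV hardly matters.

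| R | r | g | BWuc → BWint | Significant | Of these, larger absolute gap |
|---|---|---|---|---|---|
| 0.8 | 1.0 | 1.8 | −0.20 → +0.44 | about 63% | about 81% |
| 0.5 | 1.0 | 1.8 | −0.50 → −0.10 | 52-53% | about 1% (99% smaller) |
| 0.5 | 1.5 | 1.8 | −0.50 → −0.15 | 58-59% | about 1% (99% smaller) |
| 0.8 | 1.6 | 1.19 | −0.20 → −0.08 | about 10% | about 17% |

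Hand check of row 1: expected totals are 60, 48, 60 and 86.4, so SE = √(1/60+1/48+1/60+1/86.4) = 0.256. Then ln 1.8/0.256 = 2.29, and P(Z > 1.96−2.29) = 63%.

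Row 4 is the largest interaction possible if both race-specific rate ratios lie in 1.6 to 1.9: 1.9/1.6 = 1.19. The true gap there shrinks, so the 17% is sampling error in the estimated gaps.

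**4. Is scale the cause?** On the ratio scale, row 1 moves from 0.80 to 0.8×1.8 = 1.44. That is also farther from 1 (absolute logs 0.22 and 0.36), and 66-68% of significant trials show it. The failure due to scale alone is widening without reversal. At R 0.6, r 1.8, g 1.1 (−0.40 to −0.61) only about 5% of trials are significant.

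**5. Precision of the gap.** From unadjusted clinician-level differences, the mean 95% half-width for BWint − BWuc is 0.47 to 0.60 across scenarios. In row 1, the intervals for BWuc (below zero) and BWint (above zero) together show a reversal in only about 21% of significant trials.

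**The case against.** The strongest reply is that Aim 2 was framed in relative terms. SAP F.2 refers to relative differences in the intervention effect, and the power section does the same. A test of λ3 fits that framing and is valid for it. The Protocol also says differences will be interpreted against prior literature on clinically meaningful change, so significance is not the only guide. This stands, and it is why the test should not change. It does not rescue the gloss: the section that contains it defines the disparity as a difference in means.

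A second reply is that disparity means poorer communication with Black patients, so a reversal counts as success. The documents do not define disparity by its absolute size, and treating a Black advantage as an enlarged disparity is a reading brought to them. But they do not say that a reversal counts as a reduction either, and a reader of the results needs to know which happened.

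Third, row 1 is a chosen case. It assumes no benefit in White patients, contrary to Hypothesis 1a. Its Black-patient rate ratio of 1.8 is inside the SAP's 1.6 to 1.9, but its White-patient ratio is not. Those figures are detectable values, not expected effects, so they neither establish the case nor exclude it. It remains an illustration.

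A reader might infer that the mismatch between log-ratio and difference scales is the main fault. Steps 3 and 4 do not support this: the main failure is reversal, which occurs on both scales. The linear model for Hypothesis 2b has no scale mismatch, yet its gap can reverse too.

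**Conclusion.** The point holds in limited form. The λ5 label is an error and needs correction, although the surrounding sentence makes clear that the interaction is meant. The gloss claims more than a positive λ3 can show, and the plan omits the estimate that would support it.

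How often this would mislead depends on R, which the documents do not give. Of significant trials, those with a larger absolute gap range from about 1% (R 0.5, g 1.8) to about 81% (R 0.8, r 1.0, g 1.8). These figures assume 20 clinicians per arm, 3 encounters per race per clinician and no covariate adjustment.

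Two stronger readings are not supported. A reader might conclude that the 2a test is invalid; it remains a valid test of relative improvement. A reader might also conclude that a significant result will usually misstate the disparity; with a large usual-care gap it rarely does. The Protocol and SAP call 1a the primary hypothesis, so the interpretive part is one to consider rather than a required change.

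**What to change.** 1. State in SAP F.3 that Hypothesis 2a is tested on λ3.
2. Replace the gloss with: *a greater relative improvement for Black patients than for White patients*.
3. Report BWuc, BWint and BWint − BWuc with 95% intervals, and read any statement on the size or direction of the disparity alongside them. Calculate them as marginal means, averaged over pre-period mean, clinician sex, clinician type and the random intercept. Setting a log-normal intercept to zero understates both gaps by a factor √(1+CV²), which is 1.02 to 1.12 for CV 0.2 to 0.5. A difference of exponentials is not a linear contrast of coefficients, so the SAP should name a delta-method or bootstrap step.

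Do not add a rule that sorts results into reduced, unchanged, reversed or enlarged, or a pass/fail gate. *Unchanged* would need a margin that the plan does not have. Intervals that show a reduction and also exclude reversal occur in under 1% of significant trials even when the reduction is real (R 0.5, g 1.8).

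The cost is a few words and some post-estimation code, with no new data and no change to the test. The downside is wide intervals, about ±0.5 to ±0.6 for the difference in an unadjusted approximation, so the wording on disparity will be less definite.

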General considerations: All variables will be described and explored using frequency tables, means, medians, standard deviations, histograms, box plots, and trajectory plots, both overall and within clinician. The primary analyses will be conducted on an intention-to-treat basis; clinicians and patients will be analyzed in the group to which they were randomized, regardless of clinician intervention adherence, using all available data. The main conclusions drawn from this trial will be based on the pre-specified hypotheses outlined below and will be tested with two-sided p-values at the standard 0.05 level. For all study outcomes, we will interpret differences between groups over time with reference to prior literature regarding clinically meaningful changes. Results from exploratory analyses will be interpreted with appropriate consideration for their exploratory nature. Statistical analyses will be performed using the latest release SAS for Windows (Cary, NC) and R/Rstudio.

The goal of the primary Hypothesis (1a) is to determine the efficacy of the clinician communication coaching intervention versus usual care on improvement in an objective measure of the quality of communication from baseline to post-training. Additionally, we are interested the intervention effect within Black patients and White patients separately. The quality of communication will be assessed at both baseline encounters and post-training encounters by a summary of clinician-encounter counts derived from the audio recordings. We plan to use mixed-effects models as our primary analytic strategy because they will appropriately account for the intracluster correlation of multiple patient encounters for each clinician and same clinicians followed over time. The mixed-effects model for Hypothesis 1a will have the following form: $\log(\mu_{ijk}) = \mu_0 + \mu_1(post) + \mu_2(post*int_k) + \mu_3(clinrace_k) + b_{0k} + b_{1kj}$, where Y_{ijk} is the number of quality communication statements for patient i at time j clustered within physician i , and Y_{ijk} is assumed to be Poisson with mean and variance equal to μ_{ijk} . The fixed effects in the model include indicator variables for the post-treatment ($post$), intervention group (int), and clinician race ($clinrace$). The random intercepts, b_{0k} and b_{1kj} , are normally distributed and account for dependence of encounters within clinicians, both between patients and on clinicians over time. PROC GLIMMIX (with

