Aim 1: Overall intervention versus usual care	40 (20 in each treatment arm)	240 (6 per clinician)	0.2 0.35 0.5	1.5 1.6 1.8	0.01 0.05 0.1	0.37 0.41 0.44
Aim 1: Racial subgroup intervention versus usual care	40 (20 in each treatment arm)	120 (3 per clinician)	0.2 0.35 0.5	1.6 1.8 1.9	0.01 0.05 0.1	0.52 0.54 0.56
Aim 2: Racial differences in intervention versus usual care	40 (20 in each treatment arm)	Effective sample size is 60 (1 or 2 per clinician)	0.2 0.35 0.5	1.8-2.2 1.9-2.3 2.1-2.5	0.01 0.05 0.1	0.65-0.91 0.66-0.91 0.67-0.91

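### For Hypothesis 2b (and 2a), a significantly positive race-by-arm coefficient is read as a reduced disparity, with no rule that the control-arm gap is unfavourable to Black patients or that the absolute gap is smaller under coaching

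*SAP*

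**What the plan says.** Hypothesis 2b, in SAP F.3 and in the protocol's Aim 2 analyses, is a claim about size: the racial disparity in IPC will be lower with coached clinicians than with control clinicians.

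- **Rule for 2a.** The hypothesis is supported if an interaction coefficient is significantly greater than zero. SAP F.3 explains this as a larger arm difference "for Black patients as compared to White patients (i.e., the intervention group reducing the racial disparity". (The SAP calls this coefficient lambda_5. In its own equation lambda_5 is the clinician-sex term and the Black-by-arm term is lambda_3.)
- **Arm-specific gaps for 2a.** F.3 defines BW_uc and BW_int as signed Black-White differences in the control and intervention arms. No decision rule uses either.
- **Text for 2b.** A linear mixed model of the same kind "will be used to examine the reduction in racial disparities of quality of patient-centered care and test Hypothesis 2b". The only further note is that coefficients become differences in means.
- **Size and level.** The SAP's power section gives 80% power for effect sizes of "0.65 to 0.91 for Hypothesis 2b". The protocol's general considerations say hypotheses are "tested with two-sided p-values at the standard 0.05 level".

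**The concern.** The hypothesis is about the size of a gap, but the test is about the direction in which a signed gap moves. The two agree when Black patients in the control arm score lower and the shift does not carry the gap past parity to a larger size on the other side. They disagree in three situations: there is no control-arm gap and coaching creates one; the gap reverses and ends up larger; or the control gap already favours Black patients and widens. In each, the coefficient is positive and meets the criterion set for 2a.

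Nothing else in the plan supplies the missing condition. Neither document gives an IPC gap. The background evidence for worse communication with Black patients comes from recorded physician behaviour in primary care, not from IPC scores in these clinics. Baseline IPC data are left out of the analysis (stated for 1b), so no pre-period gap anchors the direction. Repeating 1b by race compares arms within a race and never compares gaps. At stake is Aim 2's conclusion that coaching reduced racial disparities.

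**Working it through.** **Inputs.** Two-sided 0.05 (protocol, general considerations). 80% power and detectable effects by ICC 0.01, 0.05, 0.1 of "0.65-0.91 0.66-0.91 0.67-0.91" (SAP power table). Clinicians: "40 (20 in each treatment arm"). Aim 2 sample: "Effective sample size is 60 (1 or 2 per clinician"). There are 240 post-period patients, about half Black by the protocol's sampling plan, so 240/4 = 60 per race-by-arm cell. Control-arm gaps are assumptions, shown as a range.

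**Step 1: the plan's own figure.** For two means in a cluster design, SE = sqrt(2 x [1 + (m-1) x ICC] / n per arm), with a t test on 40 - 2 = 38 df.
- m = 2, n = 40, ICC 0.01: SE = sqrt(2 x 1.01/40) = 0.225. The detectable effect is 0.646; at ICC 0.05 and 0.1 it is 0.659 and 0.674. Stated: 0.65, 0.66, 0.67.
- m = 1, n = 20: SE = sqrt(2/20) = 0.316. The detectable effect is 0.909. Stated: 0.91.

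The power figures reproduce and are not in question.

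**Step 2: what the coefficient measures.** Let G_uc and G_int be the Black-White gaps in the control and intervention arms, and D = G_int - G_uc the Black-by-arm coefficient. For positive D, |G_int| < |G_uc| requires G_uc < 0 and D < 2|G_uc|, that is, G_uc < -D/2. At D = 0.65 this is -0.325; at D = 0.91 it is -0.455.

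**Step 3: precision.** The clinician intercept cancels within clinician.
- SE of one arm's gap = sqrt((1-ICC) x 2/60) = 0.182 to 0.173 SD (ICC 0.01 to 0.1).
- SE of D = sqrt((1-ICC) x 4/60) = 0.257 to 0.245 SD.
- Smallest significant D = 1.96 x SE = 0.50 to 0.48 SD.

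**Step 4: how often a significant result goes with a larger absolute gap under coaching.** The arm gaps are drawn as independent normals at ICC 0.01. Two assumptions about the true effect are set side by side.

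| True control gap (SD) | Share if true shift is 0.7 SD | Share if coaching exactly closes the gap |
|---|---|---|
| 0 | 100% | not applicable |
| -0.1 | 97% | 35% |
| -0.2 | 88% | 22% |
| -0.3 | 65% | 12% |
| -0.5 | 12% | 3% |

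Power in the 0.7 SD column is 78%. In the closure column power is Phi(D/0.257 - 1.96): 6%, 12%, 21% and 49% going down. The overall chance of a significant result with a larger gap is the product, for example 0.12 x 0.22 = 0.026, and it does not exceed about 2.6% in any of these rows.

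**Step 5: the rule with and without the missing condition.** Simulated with 40 clinicians, 3 Black and 3 White patients each, ICC 0.05, true shift 0.72 SD, and a t test on clinician-level gaps.

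| Control gap to intervention gap (SD) | Positive and significant | Also estimated G_uc < 0 and smaller absolute gap |
|---|---|---|
| -0.72 to 0 (closed) | 79% | 79% |
| -0.36 to +0.36 (reversed, same size) | 80% | 40% |
| -0.20 to +0.52 (reversed, larger) | 80% | 8% |
| 0 to +0.72 (newly created) | 80% | 0.2% |
| +0.20 to +0.92 (widened) | 80% | 0% |

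The interaction test alone cannot tell these five situations apart.

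**The case against.** **The sign rule is not written for 2b.** This is right. It names 2a and reaches 2b only because the 2b model is described as similar. A reader might infer that the plan commits itself to reporting any positive 2b interaction as success; strictly, 2b has no stated decision rule. Carrying the 2a rule over is the natural reading, but it remains an inference. If it is rejected, 2b has no criterion for a reduced disparity at all, and the same added text is needed.

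**If the 2a rule carries over, so do the arm-specific gaps.** Estimating BW_uc and BW_int would let an analyst see a zero or reversed gap. That stands as far as it goes, but they are written only for 2a and nothing says what to conclude from them.

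**The hypothesis has a stated direction.** Aim 2 presumes worse communication with Black patients, so a control gap at or above zero lies outside its premise. That lowers the likelihood of the worst cases. It does not exclude them for IPC, nor does it deal with a reversal.

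**The large percentages depend on a fixed 0.7 SD shift.** Because the smallest significant shift is about 0.5 SD, a reader might infer that overshooting parity is the usual outcome unless the control gap is large. The documents do not support that. The 0.65 to 0.91 SD are detectable effects, not expected ones, and significant results are selected towards negative estimated control gaps. Under exact closure the share is 35% at most over the range shown; with half closure (-0.4 to -0.2) it is about 1%.

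**A rule based on point estimates is noisy.** This also stands. For a true narrowing from -0.4 to +0.3 SD, about 35% of significant results would fail the added condition. For an equal-sized reversal the added condition is still met, and a reduction declared, in 40% of trials.

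**Conclusion.** The point holds as a gap between the stated inference and the hypothesis. A significantly positive race-by-arm coefficient shows that the gap moved in favour of Black patients; it shows a smaller disparity only if the control gap is below zero and the shift is less than twice its size. Neither document checks this, for 2b or for 2a, where the rule is explicit. (In the 2a Poisson model the same condition applies to the log of the Black/White rate ratio.)

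How often this would mislead depends on a control gap that the documents do not give. It is most of the significant results if the true effect itself creates or reverses a gap, and a minority if coaching only closes one. The figures assume 60 patients per race-by-arm cell, complete data and the SAP's random-intercept model. The issue is one of interpretation; sample size and power are unaffected. IPC is a secondary outcome, but 2b is half of Aim 2, so the wording should be settled before the analysis.

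**What to change.** In SAP F.3:

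1. Write out the 2b model and name the Black-by-arm coefficient as the test. Do the same for 2a.
2. Estimate the model-based Black-White difference in each arm and report both with 95% CIs.
3. State that a significant positive interaction is called a reduced disparity only when the estimated control-arm difference is unfavourable to Black patients and the estimated absolute difference is smaller in the intervention arm. Otherwise report that the gap changed, and give both arm gaps and their CIs.

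**Cost.** SAP wording and two ESTIMATE statements per model; no new data. Where the gap truly closes (-0.72 to 0 SD) almost nothing is lost (79% either way). The drawback is imprecision: each arm's gap has an SE of about 0.18 SD, so some true but modest reductions that overshoot parity will be reported only as a change. The CIs let readers judge those cases.

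### The Hypothesis 1b detectable effect sizes appear to rest on patient-level degrees of freedom, while the Hypothesis 2b row fits clinician-level ones; on 38 df the printed 1b values give 77.4% to 79.1% power, not 80%

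*SAP*

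**What the plan says.** The SAP, under Power and Sample Size Considerations, bases Hypotheses 1b and 2b on a comparison of two means in a cluster randomized design, computed in PASS 15. For 1b it states: "and a type-I error of 5%, we will have 80% power to detect mean differences of effect size 0.37 to 0.44" in the overall test, and the full pair of ranges is "0.37 to 0.44 for Hypothesis 1b in the overall test, 0.52 to 0.56 for Black or White patients separately". Protocol F.5 gives the same ranges.

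The SAP table gives the cells behind these ranges, for 20 clinicians per arm and ICC 0.01, 0.05 and 0.1:

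- Aim 1 overall, 6 patients per clinician: 0.37, 0.41, 0.44.
- Aim 1 by race, 3 patients per clinician: 0.52, 0.54, 0.56.
- Aim 2 (Hypothesis 2b), 1 or 2 patients per clinician: "0.65-0.91 0.66-0.91 0.67-0.91".

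The Protocol's general considerations say that hypotheses "will be tested with two-sided p-values at the standard 0.05 level", and its Design & Procedures section makes the clinician the unit of randomization. The 1b model in the SAP (F.2) is a linear mixed model with a clinician random intercept and two clinician-level stratification covariates, fitted in PROC MIXED. No row of the table has a stated df basis, and no denominator-df method is named for PROC MIXED.

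**The concern.** The intervention indicator varies only between clinicians. With 40 clinicians, the comparison of arms has 38 degrees of freedom, or 36 if each of the two clinician covariates is binary. The design effect corrects the standard error for clustering but not the critical value. If that value comes from a t distribution with 238 or 118 df, the test is treated as if there were that many independent units, and the detectable effect comes out slightly too small.

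The Aim 2 row of the same table seems to use the smaller df. If so, the rows are not on one footing, and the 80% claim for the secondary outcome is a little optimistic, both overall and within each race.

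**Working it through.** **Inputs.** Two-sided 5% (Protocol, general considerations); 80% power, 20 clinicians per arm, 6, 3, or 1 to 2 patients per clinician, and ICC 0.01/0.05/0.1 (SAP power text and table). Effect sizes are in SD units, so SD = 1. The df is the only unstated input.

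**Formula.** With m patients per clinician, SE = sqrt(2 × [1 + (m − 1) × ICC] / (20 × m)). Power is taken from the noncentral t distribution with noncentrality (effect size)/SE and the chosen df.

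Example, m = 6, ICC = 0.01: SE = sqrt(2 × 1.05 / 120) = 0.1323. With 238 df, 80% power needs an effect of 0.3721. With 38 df it needs 0.3803.

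**Step 1: reproduce the Aim 1 rows.** Effect size for 80% power:

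| m | ICC | Printed | Patient-level df (238 or 118) | 38 df | 36 df |
|---|---|---|---|---|---|
| 6 | 0.01 | 0.37 | 0.3721 | 0.3803 | 0.3809 |
| 6 | 0.05 | 0.41 | 0.4060 | 0.4150 | 0.4156 |
| 6 | 0.1 | 0.44 | 0.4448 | 0.4546 | 0.4552 |
| 3 | 0.01 | 0.52 | 0.5208 | 0.5301 | 0.5309 |
| 3 | 0.05 | 0.54 | 0.5409 | 0.5505 | 0.5513 |
| 3 | 0.1 | 0.56 | 0.5649 | 0.5750 | 0.5758 |

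Patient-level df match all six printed values. With 38 df only one matches: 0.41, where the unrounded value is 0.41496. A normal approximation matches five of six (it gives 0.404 against 0.41).

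**Step 2: reproduce the Aim 2 row.**

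| m | ICC | Printed | Patient-level df (78, or 38 at m = 1) | 38 df |
|---|---|---|---|---|
| 2 | 0.01 | 0.65 | 0.6375 | 0.6461 |
| 2 | 0.05 | 0.66 | 0.6500 | 0.6587 |
| 2 | 0.1 | 0.67 | 0.6653 | 0.6742 |
| 1 | all | 0.91 | 0.9091 | 0.9091 |

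Here 38 df match every cell. With 78 df, the first two cells would print as 0.64 and 0.65. The 0.67 cell fits both choices, and at m = 1 the two choices coincide. The normal approximation fails throughout this row (0.630/0.642/0.657 and 0.886).

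**Step 3: look for one rule that gives the whole table.** Patients minus clinicians (200, 80 and 40 df) gives 0.645/0.658/0.673 for m = 2, which fits. It also gives 0.4451 and 0.5672 where the Aim 1 rows print 0.44 and 0.56, and it leaves no df at m = 1. None of the rules tried reproduces both sets of rows.

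**Step 4: power at the printed Aim 1 values.**

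| Printed | Patient-level df | 38 df | Loss from df alone |
|---|---|---|---|
| 0.37 | 79.55% | 77.81% | 1.74 points |
| 0.41 | 80.76% | 79.05% | 1.71 |
| 0.44 | 79.15% | 77.39% | 1.76 |
| 0.52 | 79.87% | 78.47% | 1.40 |
| 0.54 | 79.87% | 78.47% | 1.40 |
| 0.56 | 79.31% | 77.90% | 1.41 |

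The rest of each gap from 80% is two-decimal rounding of the printed value. At 0.44 the gap is 80 − 77.39 = 2.61 points, of which 80 − 79.15 = 0.85 is rounding. At 0.41 rounding works the other way and offsets part of the df loss. With 36 df, power at the printed values is 77.3% to 78.9%.

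**The case against.** **The mixture is inferred.** The documents name a method and a software package but no df. Only two Aim 2 cells, 0.65 and 0.66, separate the two choices, each by 0.01. This stands: the finding is an apparent inconsistency, and the sponsor's PASS output would settle it. It does not remove the power shortfall, which follows from 38 df however the figures were produced.

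**The printed values are reproducible.** Patient-level df with a design effect return all six Aim 1 values, so nothing was miscalculated on that basis. This also stands. The issue is the choice of df and its consistency across rows, not a slip of arithmetic.

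**Part of the shortfall is rounding.** True, as the last table shows. By the same strict standard, the Aim 2 value 0.67 gives 79.5% at 38 df.

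**Forty clinicians is a floor.** The Protocol recruits up to 50 to secure at least 40 with complete measures. With 42 clinicians (21 per arm, 40 df), power at the printed values is 79.5% to 81.1%; with 44 it is 81.4% to 82.9%. So the trial may well reach 80% in practice. The table, however, states its figures for exactly 40, and those are the figures to correct.

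**The effect is small beside the ICC uncertainty.** Across the plan's own ICC range, the overall detectable effect moves by 0.44 − 0.37 = 0.07, against about 0.01 for the df. This is fair, and it limits the weight of the point.

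**Conclusion.** The point holds as a small inconsistency. On clinician-level df, the Hypothesis 1b effect sizes give 77.4% to 79.1% power for 40 clinicians instead of the stated 80%. Detectable effects rise by about 0.01, and five of the six Aim 1 cells change at two decimals. This rests on the table's inputs (20 clinicians per arm, equal cluster sizes, the stated ICCs) and on 38 df as the basis for a comparison between clinicians. The 36 df variant further assumes that both stratification covariates are binary, which the documents do not say.

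A reader might go further in three ways that the documents do not support:

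- That the plan ignores clustering. It does not: the printed values include the design effect.
- That every Aim 1 cell is printed too favourably. At 38 df the 0.41 cell still prints as 0.41.
- That the secondary analysis is materially underpowered. The shortfall is at most 2.6 points, part of it rounding, and two clinicians above the floor roughly remove it.

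**What to change.** Use clinician-level df in every row of the 1b/2b columns and state that basis. Then restate Hypothesis 1b in the SAP power text, the SAP table and Protocol F.5:

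- At 38 df: 0.38/0.41/0.45 overall (0.38 to 0.45) and 0.53/0.55/0.57 by race (0.53 to 0.57).
- At 36 df, if the two stratification covariates are binary and are counted: 0.38 to 0.46 overall and 0.53 to 0.58 by race.

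Round once from the unrounded result: at 38 df the upper ends are 0.4546 and 0.57498, which print as 0.45 and 0.57. Name the denominator-df method for PROC MIXED in the 1b analysis, so that the test and the power basis agree.

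The cost is one rerun of the power software and a few edited figures, which become slightly less favourable for a secondary outcome. Sample size and design stay as they are.
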